## **Study Protocol and Statistical Analyses Plan**

Recent studies have shown that C natriuretic peptide (CNP) is produced from granulosa cells, increasing cumulative guanosine monophosphate (cGMP) production by affecting cumulus cells through natriuretic peptide receptors. It is suggested that produced cGMP maintains the transport of oocytes via the gap junctions and leads to a continuous increase in cyclic adenosine monophosphate (cAMP) levels in the oocyte. An important role of increased internal cAMP levels in the oocyte is shown to suppress meiotic progression.

Deoxyribonucleic acid studies in animals have shown that expression of the natriuretic peptide precursor increases during the periovulatory period and shows that this increase decreases rapidly after luteinizing hormone (LH) / human chorionic gonadotropin (hCG) stimulation. Human studies have shown that after ovulation induction, the CNP level in follicular fluid decreases following ovulatory dose of hCG. Polycystic ovary syndrome (PCOS) is the most common endocrine disease in the reproductive period, characterized by hyperandrogenism, oligo-anovulation, and polycystic ovarian morphology on ultrasonography. Recently, a study on PCOS-like mouse model investigated the effect of CNP/ natriuretic peptide receptor 2 (NPR2) on oocyte maturation and anovulation. They increased the expression of CNP/NPR2 with hyperandrogenism and showed meiotic arrest and anovulation in the subject oocytes. Conversely, they showed that reducing CNP/NPR2 production led to partial recovery of ovulation. CNP serum level is thought to show differences between healthy women and women with polycystic ovary syndrome.

In the light of these data, we conclude that in PCOS, which is known to be associated with hyperandrogenism and anovulation, serum levels of CNP, which is also associated with these components, may be elevated. In this study, it was aimed to determine serum CNP levels in PCOS patients, their relationship with serum androgens, and comparison with the healthy group.

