In this prospective study, a total of 66 patients admitted to the Department of Obstetrics and Gynecology of the Near East University Hospital were included. PCOS group consisted of 36 women and control group included 30 healthy women with regular menstruation aged between 18-40 years old. PCOS diagnosis was made according to Rotterdam criteria. PCOS diagnosis was made in the presence of two or three of these findings; oligo/anovulation, polycystic ovaries on ultrasonography and clinical or biochemical manifestations of hyperandrogenism.

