# Comparison of Serum C Type Natriuretic Peptide Levels Between Polycystic Ovary Syndrome Patients and Healthy Women

NCT04006171

Date:01.07.2021

Age, body mass index (BMI), serum levels of LH, follicle stimulating hormone (FSH), estradiol, thyroid stimulating hormone (TSH), prolactin (PRL), androstenedione, dehydroepiandrosterone sulfate (DHEAS), total testosterone, free testosterone, sex hormone binding globulin (SHBG), total cholesterol (TC), triglyceride (TG), high density lipoprotein (HDL), low density lipoprotein (LDL), glucose and insulin levels were measured. For insulin sensitivity, homeostatic model of insulin resistance (HOMA-IR) was used. Free androgen index (FAI) was calculated for all participants.

Exclusion criteria were as follows: age over 40 years, current pregnancy, hyperprolactinemia, thyroid disease, congenital adrenal hyperplasia, a history of ovarian surgery or any other systemic disease or drugs that could influence hypothalamic pituitary ovarian axis, androgen production, insulin and or/glycemic metabolism, patients with cardiac or renal disease and therefore drug use, patients who received any hormone therapy including contraceptives up to 6 months before study.

Morning fasting venous blood samples were taken from the patients on the 2nd or 3rd day of the menstruation for all participants. All blood samples were centrifuged on the day of collection and separated serum samples and were kept at -80 degrees celcius until the day of CNP test. Serum CNP levels of the patients were analyzed by an enzyme-linked immunosorbent (ELISA) assay for human CNP in accordance with the manufacturer's instructions (SEA721Hu, ELISA Kit for Human CNP, Wuhan USCN Business Co., Ltd., Cloud-Clone Corp., CCC, USA).

Data were analyzed using Statistical Package for Social Sciences software (SPSS v15, SPSS Inc, Chicago, IL, USA). Data were presented as mean±standard deviation or median and interquartile range. Independent t-test was used to compare the parameters with normal distribution. Parameters that don't fulfill the parametric test assumptions were compared using Mann-Whitney U test. Correlation of CNP with other parameters was analyzed using Spearman's rank correlation test. Receiver operating characteristic (ROC) curve was used to evaluate diagnostic sensitivity and specificity of CNP for PCOS. P values less than 0.05 were regarded as statistically significant.

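### One flat p<0.05 rule covers CNP correlations with up to 20 parameters, with no named primary test and no stated analysis set for the androgen correlations

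*Combined protocol and SAP*

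**What the plan says.** The last paragraph of the introduction gives the aim: "it was aimed to determine serum CNP levels in PCOS patients, their relationship with serum androgens, and comparison with the healthy group". The study population paragraph gives the sizes, "PCOS group consisted of 36 women and control group included 30 healthy women", and lists "clinical or biochemical manifestations of hyperandrogenism" among the three findings of which two are needed for a PCOS diagnosis.

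The statistical analysis paragraph is wider than the aim. Groups are compared by t-test or Mann-Whitney on the parameters in general, without singling out CNP. For the correlations it says only "Correlation of CNP with other parameters was analyzed using Spearman's rank correlation test". It adds a diagnostic analysis: "Receiver operating characteristic (ROC) curve was used to evaluate diagnostic sensitivity and specificity of CNP for PCOS". It closes with "P values less than 0.05 were regarded as statistically significant".

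The document names no primary test, testing order, multiplicity rule or exploratory label. It does not list the parameters to be correlated with CNP, or say whether those correlations use the PCOS women, the controls or both.

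**The concern.** There are two separate problems.

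**Multiplicity.** The aim singles out the androgens, but the significance rule does not. A chance p<0.05 for CNP with TSH, prolactin, a lipid or glucose would be called significant on the same terms as a testosterone result.

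**Analysis set.** Hyperandrogenism helps to define PCOS, and the introduction expects CNP to be higher in PCOS. If both groups are pooled, CNP and androgens can move together simply because both differ between groups. A significant pooled correlation could then restate the group difference while being read as evidence of a relationship between CNP and androgens, which is a stated aim of the study.

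**Working it through.** The plan has no derived figure to reproduce (no power, sample-size or overall error calculation). The only stated figure is the 0.05 threshold. It is taken as two-sided, which the plan does not state.

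**1. Number of correlations.** The measurements paragraph names:
- age, BMI, LH, FSH, estradiol, TSH and prolactin (7);
- androstenedione, DHEAS, total and free testosterone, and SHBG (5);
- four lipids, glucose and insulin (6).

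That is 18 measured. HOMA-IR and FAI ("Free androgen index (FAI) was calculated for all participants") bring the total to 20. This is a maximum, because the plan does not say which are used. Five are androgen measures: total testosterone, free testosterone, androstenedione, DHEAS and FAI. SHBG is arguable.

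**2. False positives at 0.05 each.** Expected number = m × 0.05, whatever the dependence. Chance of at least one under independence = 1 − 0.95^m. The last column comes from simulation under assumed correlation structures, because the documents give none.

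| Situation | m null | Expected | At least one, independence | At least one, assumed correlations |
|---|---|---|---|---|
| All correlations null | 20 | 1.00 | 1 − 0.95^20 = 64% | about 30–60% |
| Androgens real (rho 0.35), rest null | 15 | 0.75 | 1 − 0.95^15 = 54% | about 38–50% |
| Androgen family, all null | 5 | 0.25 | 1 − 0.95^5 = 23% | about 15–21% |

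The results are nearly the same at n=66 and n=36. Overlap is certain for some parameters (FAI is built from total testosterone and SHBG, HOMA-IR from glucose and insulin), so the independence figures are upper values.

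**3. Effect of pooling 36 and 30 women.** Suppose there is no CNP–androgen correlation within either group, and let d be the group difference in within-group SDs. With f = (36 × 30)/66² = 0.248, the correlation induced by pooling is

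r = f·d_CNP·d_A / √[(1 + f·d_CNP²)(1 + f·d_A²)].

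For d_CNP = 0.8 and d_A = 1.0: r = 0.198 / √(1.159 × 1.248) = 0.165. The critical |rho| at n=66 is 0.242 at p=0.05.

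Simulated Spearman tests, with androgens correlated 0.5 within group:

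| d_CNP / d_A (assumed) | Mean pooled rho | One androgen p<0.05 | Holm on five, at least one |
|---|---|---|---|
| 0.5 / 0.5 | 0.06 | 7% | 7% |
| 0.5 / 1.0 | 0.11 | 14% | 14% |
| 0.8 / 1.0 | 0.17 | 27% | 29% |
| 1.0 / 1.0 | 0.20 | 37% | 42% |
| 1.0 / 1.5 | 0.28 | 62% | 66% |

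Holm does not help, because the pooled correlation is real and merely answers a different question. Adjusting the ranks for group brings the last two columns back to about 5% and 4% in the same model.

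**4. Power cost of Holm.** Fisher z with variance 1.06/(n − 3), rho = 0.35, atanh(0.35) = 0.365. The strictest step for five tests is 0.05/5 = 0.01.
- n=36: SE = √(1.06/33) = 0.179 and 0.365/0.179 = 2.04. Power is Φ(2.04 − 1.96) = 53% at 0.05 and Φ(2.04 − 2.58) = 30% at 0.01.
- n=66, group-adjusted: SE = √(1.06/62) = 0.131. Power is 80% at 0.05 and 59% at 0.01.

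**The case against.** **The main test is obvious.** The title is a comparison of CNP between PCOS and healthy women, and the hypothesis is that CNP may be elevated in PCOS. This largely stands. A reader might infer from the missing primary test that the CNP comparison is itself inflated. It is not: it is one identifiable test at 0.05. What is missing is the statement that sets it apart.

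**The aim already points to PCOS women.** The aim speaks of CNP levels in PCOS patients and then of their relationship with androgens; the healthy group enters only for the comparison. This also stands. A reader might infer that the plan pools all 66 women, but the document does not say so. It leans the other way in the aim and leaves the matter open in the analysis paragraph, where "Correlation of CNP with other parameters was analyzed using" a named test carries no restriction. Pooling is permitted, not planned.

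**The sizes are assumed.** True. The document gives no SDs, group differences or correlations, and the pooling result runs from near nominal to severe depending on the assumed effects.

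**The rule also covers up to 21 group comparisons.** With the 20 correlations that makes 41 tests, and 1 − 0.95^41 = 88% is a tempting headline. It would need every comparison to be null, which is implausible when one group is selected partly for hyperandrogenism.

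**Restricting to PCOS is not a perfect remedy.** A woman can qualify through anovulation, which the introduction links to CNP, or through hyperandrogenism. Conditioning on the diagnosis can therefore distort the CNP–androgen correlation. This stands as a limitation.

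**An exploratory study needs no adjustment.** That would be a fair position if the plan took it. It does not use the label, and it declares significance.

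**Conclusion.** The point holds as a limit on how the correlations may be read. Followed as written, the rule yields on average one chance finding per 20 null correlations. The chance of at least one is 64% at most, and roughly 30–60% under assumed dependence. The count of 20 and the independence figures follow directly from the document.

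The pooling problem is conditional. If the groups are pooled without adjustment, one androgen reaches p<0.05 in 7–62% of studies with no within-group association, given assumed differences of 0.5–1.0 SD in CNP and 0.5–1.5 SD in androgens. The mechanism is firm; the size rests wholly on those assumptions.

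The point does not undermine the CNP group comparison. The plan is written in the past tense, from which a reader might infer that tests were chosen after seeing results. The document does not show that, but it leaves open whether an ordering added now would be prespecified. The change should be made; the plan is not invalid without it.

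**What to change.** - **Primary:** name the CNP comparison between PCOS and control women as the single primary test, two-sided 0.05.
- **Secondary:** list CNP with total testosterone, free testosterone, androstenedione, DHEAS and FAI as the only secondary correlations. Analyse them in the 36 PCOS women, in line with the aim, with the group-adjusted rank correlation in all 66 as support. Do not use unadjusted pooled correlations as the test.
- **Error control:** apply Holm to these five if significance is to be claimed, or report them as exploratory with 95% confidence intervals. The family of five is a judgement. If SHBG is counted as androgen status, list six.
- **Everything else:** report the other correlations, the other group comparisons and the ROC analysis as exploratory, with estimates and 95% confidence intervals and no significance claims.
- **Limitation:** state that within-PCOS and group-adjusted correlations still condition on a diagnosis partly defined by hyperandrogenism.
- **Timing:** if results were already known, disclose the ordering as post hoc. It then gives no prespecified error control.

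**Cost:** SAP wording, five Holm-adjusted p-values and one partial correlation on ranks per androgen. No new data are needed, and the primary test loses nothing. Fewer results will be called significant. At Holm's strictest step, power for rho 0.35 falls from about 53% to 30% in the 36 women, and from about 80% to 59% in the group-adjusted analysis of 66. The exploratory option avoids that loss by giving up significance claims for the correlations.
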